#### **8.4. Drugs/Devices**

Sterile talc powder, as used in this trial, is a natural, asbestos-free product, supplied sterile in a single use 100 ml amber glass vial. It has been used as sclerosing agent to decrease the recurrence of malignant pleural effusions in symptomatic patients. The recommended dose is 2 to 5 grams administered intrapleurally. Common side effects following pleural administration of talc are pleuritic pain and low-grade fever. In this trial, the talc solution mixed with lidocaine will be prepared by MHS Pharmacy Department.

Cathflo activase is a naturally occurring protein that splits the inactive zymogen plasminogen into the active enzyme plasmin. It is supplied as a sterile powder (2 mg) in a single use glass vial (Cathflo®, Activase®). Following reconstitution it is stable at room temperature for up to 24 hours.(22) Given intravenously it is rapidly metabolized by the liver and undergoes biphasic elimination with an initial half-life of 3-5 minutes followed by an elimination half-life of 27-46 minutes.(23) Pharmacodynamics and bioavailability of cathflo activase in the pleural space is not known. cathflo activase in the treatment of complex pleural effusion has been evaluated in both controlled and non-controlled settings, demonstrating beneficial reductions in effusion volume, clinical symptoms, hospital stay, and the need for surgical intervention, without local or systemic bleeding. Various intrapleural dosage regimens have been used: 2 to 5 mg diluted in up to 40 mL of normal saline or 0.1 mg/kg diluted in 10 to 100 mL of normal saline.(17, 19, 24, 25). In a retrospective analysis of 46 patients at MHS treated with cathflo activase for management of complex pleural effusion, 131 doses of cathflo activase were given ranging from 2 to 6 mg. No difference in efficacy was identified between 4 and 6 mg, and therefore 4 mg was chosen as the treatment dose for this protocol (unpublished results).

## **9.0 STATISTICAL METHODS**

### **9.1. Primary and Secondary Outcome measures**

The primary outcome measure is the proportion of patients with successful pleurodesis at day 3 after administration of TSP. Successful pleurodesis is defined as “radiographically satisfactory pleurodesis” (RSP), as evidenced by 1) chest x-ray demonstrating similar or decreased amount of pleural fluid/opacification compared to day 0 (day pleurodesis is performed) and 2) drainage

of less than 100 ml of fluid over the preceding 24 hours. Chest x-ray results will be scored on a three-point scale (-1, 0, +1) based on comparison of pleural space opacification on the side of the TSP to baseline:

1. Worse (-1): Pleural space opacification is worse, suggesting residual undrained fluid or reaccumulation of loculated fluid.
2. Same (0): Pleural space opacification similar to baseline.
3. Better (+1): Pleural space opacification is better, suggesting less pleural fluid than at baseline.

The secondary outcome measures will include the following:

1. Proportion of patients with RSP at any time after TSP
2. Duration of chest tube drainage
3. Days to achieve RSP
4. Pain and dyspnea scores as assessed by a visual-analogue scale (on a scale from 0 to 100 mm, with a score of 0 indicating a complete absence of symptoms and a score of 100 maximum symptoms).
5. Proportion of patients requiring repeat pleurodesis
6. Proportion of patients requiring additional chest tube
7. Change in serum hemoglobin levels within three days of cathflo activase
8. Length of hospital stay (in days) after TSP.
9. All hospital costs associated with both treatment arms.

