### **6.1. Sample Size**

Based on review of our experience with pleurodesis, TSP can be expected to produce RSP at three days in approximately 60% of patients. We anticipate an RSP rate of approximately 80% at three days using the combination of talc and cathflo activase. Therefore, in order to detect a 20% difference in successful pleurodesis with 80% power, a 5% significance level (1-sided) and 5% loss to follow-up, a total of 136 patients (68 in each arm) will be needed in this trial.

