### **6.3. Randomization**

Subjects undergoing pleurodesis as part of their standard of care treatment, and who have signed informed consent, will undergo a stratified randomization according to effusion etiology (malignant vs. non-malignant) with the use of a computer-based system in a 1:1 ratio. A statistician will randomly generate treatment allocation codes (randomization lists for either placebo or cathflo activase) according to study design specifications as determined by the statistician and principal investigator. The treatment allocations will be given to pharmacy with sealed opaque envelopes. Once a subject has consented to enter the trial and is ready for pleurodesis an envelope will be opened and an independent pharmacist (researcher) will prepare the drug or placebo in a syringe labeled with “study drug” and the randomization code according to the treatment allocations. Syringes containing placebo or cathflo activase (study drug) cannot be distinguished because both preparations are clear and colorless and have the same volume. The prepared syringe labeled “study drug” will be brought to the bedside by the pharmacist and nurse and the subject will then be given the allocated treatment regimen. The subject’s ID, date, time and randomization code will be recorded. The doctor/nurse and subject will not know which drug was injected (double blinded). The preparer (pharmacist) will retrieve the recorded information, determine if the injection was done as planned, and save the documents in a secured place.

The envelopes should be opened just after the subject has consented to enter the trial and is ready for pleurodesis. In case of a broken or lost syringe, the preparer will use the allocation code of the envelope and the allocation log to determine whether the syringe should be replaced with placebo or study drug.

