## 8.2. Assessments/Tasks

Following consent, a baseline assessment will be undertaken pre-randomization by a member of the trial team and entered into the REDCap system hosted at Office of Human Research of MHS. The following data will be recorded prior to randomization:

1. Patient demographics and physical characteristics
2. Mode of presentation, current diagnosis, cause of effusions (if known).
3. Medical history and current medication.
4. Previous pleural interventions.
5. Symptoms, including pain and SOB according to a visual analog scale (VAS) (Appendix I, II).
6. Pleural fluid biochemical and cytological test results
7. Baseline hemoglobin (day of or day before TSP)
8. Baseline (day of or day before TSP) CxR and chest CT (if available) findings.

After randomization and TSP with or without cathflo activase, all patients will have daily follow-up until the chest tube is removed, and at 14 and 28 days, and three months after TSP. At all visits, the following data will be recorded:

1. VAS for chest pain and SOB will be documented (Appendix I, II).
2. CxR (PA and lateral preferred).
3. Drained pleural volumes in 24 hours (if the chest tube is still in place).
4. Serum hemoglobin (only for inpatient visits within three days of the pleurodesis procedure).
5. Repeat pleural interventions.
6. Chest CT scan, as justified by the principal investigator.

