## 8.3. Treatments/Interventions

The trial interventions are summarized in Figures 1 and 2 and described in detail below. The delivery of each of the treatment and its aftercare will be provided according to its usual practice protocols and are not specified in this trial. All patients will have a pigtail chest tube (size 10-14) inserted under image guidance, or PleurX® catheter placement. This is current practice for management of these patients. Prior to pleurodesis the chest tube will be managed to achieve the most complete fluid drainage possible as assessed by CxR and determined by the clinical team. In the case of uncertainty, chest CT will be used to confirm the drainage of fluid and adequate inflation of the lung.

For all subjects, talc slurry (sterile talc, 5 gm, mixed with lidocaine, 20 mg, diluted in sterile saline to a total volume of 100 mL and dispensed into two 60 mL luer lock syringes, prepared by MHS Pharmacy Department) will be instilled through the chest tube at bedside. This will be followed immediately by instillation of either placebo (arm 1: 50 mL normal saline) or study drug (arm 2: cathflo activase, 4 mg, suspended in 50 mL normal saline). This syringe will be prepared by the MHS Pharmacy Department based on the randomization results and coded so that neither the administering clinical team nor the patient will be able to discern to which arm the patient has been assigned. The chest tube will be clamped with orders written to unclamp in 12 hours and insure

the tube is connected to a pleural drainage system (e.g. Pleurevac®) set for standard suction of -20 cm H2O. Daily assessments will be performed until the chest tube is removed. These include drainage volume over 24 hours, CxR, and pain and dyspnea scores.

Drainage volume over the prior 24 hours will be recorded daily using the Bedside Pleural Drainage Record. If the volume is less than 100 cc/24 hours for day 3 (defined as the third 24-hour period following TSP) and the CxR on day 3 shows the pleural space is the same or better than baseline, then the chest tube will be removed. If the chest tube is not removed, management will be according to the algorithm in Figure 2, and may include: continued monitoring, chest CT to evaluate for residual loculated effusion, cathflo activase to evacuate undrained effusion, or repeat TSP with or without cathflo activase.

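### Secondary outcomes 1 and 3 credit the randomized arm with RSP reached after rescue, which can include cathflo in the placebo arm; a rescue-free version should be pre-specified

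*Combined protocol and SAP*

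**What the plan says.** Section 9.1 lists as secondary outcome 1 "Proportion of patients with RSP at any time after TSP" and as secondary outcome 3 "Days to achieve RSP". Neither has a time limit or a rule for success that follows a further intervention.

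Under section 8, a patient without RSP on day 3 is managed by the Figure 2 algorithm. The options listed there include continued observation, more cathflo, additional drainage tubes and repeat talc slurry pleurodesis (TSP). Section 8.3 likewise allows "cathflo activase to evacuate undrained effusion, or repeat TSP with or without cathflo activase". Neither section restricts these options by randomized arm.

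Section 9.2 does not mention rescue. Its intention-to-treat sentence concerns the primary outcome only. Numerical outcomes get a t-test by default; the log-rank test is named only for symptomatic fluid recurrence. Section 8.2 records "Repeat pleural interventions" at all visits.

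**The concern.** With no counting rule, RSP reached after rescue falls to the arm originally assigned. In the placebo arm that rescue can be the study drug. Section 3.1 suggests that such rescue could work: the investigators report that a further cathflo dose some days after TSP may help with loculations, and they favor day 3 as the time to give it.

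Two hypotheses in section 4.2 are at stake: number 2 (cathflo does not inhibit pleurodesis) and number 5 (it shortens the time to pleurodesis). For number 5, convergence of the arms can hide a benefit. For number 2 it works in the hypothesis's favor, because an outcome pulled toward equality tends to support a claim of no inhibition whether or not the claim is true. Section 3.1 itself raises the possibility that added fibrinolysis could make pleurodesis fail.

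**Working it through.** **Inputs.** Section 6.1 gives the day-3 rates: "TSP can be expected to produce RSP at three days in approximately 60% of patients" and "We anticipate an RSP rate of approximately 80% at three days using the combination of talc and cathflo activase". It also gives one-sided 5% significance, 80% power, 5% loss and 136 patients, 68 per arm. The share r of day-3 failures who later reach RSP is not in the documents; it is assumed and varied.

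**The plan's own figure.** With pooled variance and no continuity correction, n per arm = [1.645 × √(2 × 0.70 × 0.30) + 0.842 × √(0.60 × 0.40 + 0.80 × 0.20)]² / 0.20² = 63.9, so 64. Then 64 / 0.95 = 67.4, so 68 per arm and 136 in total. This matches. Power below uses the 64 evaluable per arm.

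**Any-time RSP, same r in both arms.** Placebo: 0.60 + 0.40r. Cathflo: 0.80 + 0.20r. Difference: 0.20 × (1 − r). Power = Φ{[d√64 − 1.645 × √(2p̄(1 − p̄))] / √(p₁(1 − p₁) + p₂(1 − p₂))}, where d is the difference and p̄ the mean of the two rates. At r = 0.5 this is Φ[(0.80 − 1.645 × 0.505) / 0.50] = Φ(−0.06), or 48%.

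| r (assumed) | Placebo | Cathflo | Difference (points) | Power |
|---|---|---|---|---|
| 0 | 60% | 80% | 20 | 80% |
| 0.3 | 72% | 86% | 14 | 62% |
| 0.5 | 80% | 90% | 10 | 48% |
| 0.7 | 88% | 94% | 6 | 32% |
| 0.9 | 96% | 98% | 2 | 16% |

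The last row is rough: expected failures are only 64 × 0.04 = 2.6 and 64 × 0.02 = 1.3.

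**Unequal r.** With r = 0.7 on placebo and 0.5 on cathflo, the rates are 88% and 90% (2 points). With 0.5 and 0.7 they are 80% and 94% (14 points).

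**How much is due to rescue.** Late RSP under observation belongs to the randomized treatment. Suppose r = 0.7, with 0.3 reached by observation before any rescue and 0.4 after rescue. Rescue-free RSP is 72% vs 86% (14 points); as-written RSP is 88% vs 94% (6 points). Rescue then costs 14 − 6 = 8 points, not 20 − 6 = 14. If the observation share is the same in both arms, the table is an upper bound on the loss due to rescue.

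**Masked harm (assumed rates).** Let day-3 RSP be 60% on placebo and 45% on cathflo, with r = 0.7 in both. Any-time RSP is 0.60 + 0.40 × 0.7 = 88% vs 0.45 + 0.55 × 0.7 = 83.5%. A 15-point harm shows as 4.5 points.

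**Days to RSP.** In the text, rescue starts after the day-3 assessment, so the 20-point gap on day 3 is already in the data. A simulation (1,500 runs per scenario, 64 per arm; early success on day 3, later success uniform over days 4 to 7, the rest censored at day 14) gave log-rank power of about 0.70, 0.64, 0.60 and 0.60 at r = 0.3, 0.5, 0.7 and 0.9. With no late success the log-rank test reduces to the day-3 comparison, at about 0.80. The erosion is real but much smaller than for any-time RSP.

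**The case against.** The strongest defense is that eventual RSP under the assigned strategy, rescue included, is a legitimate treatment-policy question and the natural reading of outcome 1. That stands as a reason to keep the as-written version. But the plan does not say that this is the question, and it is not the one asked by hypotheses 2 and 5.

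Other outcomes also bear on inhibition: the primary at day 3, repeat pleurodesis (outcome 5), additional tube (outcome 6), and time to symptomatic recurrence. This too stands, so hypothesis 2 does not rest on any-time RSP alone. None of these, however, counts rescue by cathflo alone or corrects outcomes 1 and 3. A rescue-free outcome has limits of its own: it depends partly on clinicians' decisions to intervene, and if nearly all failures are rescued soon after day 3 it comes close to repeating the primary.

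A reader might also infer more than the documents support:

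- **That most of the contrast is lost.** With equal r this needs r above 0.5, and no rate is given. It also treats late success under observation as rescue.
- **That 40% and 20% are rescue rates.** They are the expected day-3 failure rates; some of those patients may only be observed.
- **That days to RSP is affected as badly.** The day-3 separation comes before rescue and is kept.
- **That rescue cathflo is open-label.** The text does not say whether it is blinded.

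Figure 2 was not readable in the text used for this check and may say when each option is used. The rule for counting outcomes still belongs in 9.1 or 9.2.

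**Conclusion.** The point holds for secondary outcomes 1 and 3. As written, they credit the randomized arm with RSP reached after rescue, and that rescue can be the study drug in the placebo arm. For any-time RSP, the planned 20 points shrink to between 14 and 2, and power to between about 62% and 16%, for r from 0.3 to 0.9. This assumes the section 6.1 day-3 rates, the same r in both arms and 64 evaluable per arm. The part due to rescue is at most that size; how large it is cannot be known from the documents. Days to RSP is affected only after day 3.

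The primary outcome is read before rescue and is unaffected, and the plan claims no power for these secondary outcomes. This is an inexpensive improvement to two secondary outcomes. It does not threaten the trial's main conclusion.

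**What to change.** In 9.1 and 9.2, pre-specify two versions of outcomes 1 and 3:

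- **As written**, labelled as a treatment-policy analysis: RSP counts whatever was given in between.
- **Rescue-free**: RSP counts only if reached before any further cathflo, additional tube or repeat TSP. RSP under observation alone still counts.

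For days to RSP, replace the default t-test, which has no value for patients who never reach RSP, with a time-to-event analysis that treats rescue as a competing event. State when follow-up for this outcome ends. State that the rescue-free version will be used to interpret hypotheses 2 and 5.

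Confirm that the repeat-intervention item in 8.2 captures rescue cathflo given through an existing tube, with its date.

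The cost is SAP wording, possibly one dated data field, and one extra version of two secondary outcomes. The rescue-free result will depend partly on decisions to intervene, which is a reason to report both versions side by side. The clinical algorithm is unchanged.

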## 3.0 INTRODUCTION

A pleural effusion is an accumulation of fluid in the chest around the lung, and is a common clinical problem, with an incidence of approximately 1.5 million per year in the United States.(1) Large collections compress the underlying lung and contribute to significant morbidity by affecting a patient's ability to breathe easily. A variety of conditions contribute to the development of a pleural effusion, such as heart, kidney and liver failure, cancer, and pneumonia. Often, drainage of the effusion is sufficient. But if the underlying cause cannot be corrected the effusion will return and more definitive management is indicated. Options for definitive management of a recurring pleural effusion are either an indwelling catheter to facilitate repeated drainage (e.g. PleurX®) or pleurodesis to prevent reaccumulation of fluid by sealing the pleural space.(2-5) Pleurodesis occurs in response to inflammation, which can be intentionally induced through either mechanical/surgical abrasion or application of a chemical irritant. Chemical pleurodesis is a convenient option because it can be done by injection of the chemical in suspension through a small drainage tube into the pleural space, rather than requiring surgery. Many agents have been used to promote pleurodesis, including sterile talc, tetracycline, doxycycline, bleomycin, silver nitrate and povidone iodine.(2)

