## 8. PROCEDURES

Figure 1 shows the proposed workflow through the trial. Following the informed consent, each participant is assigned a unique study number and baseline data will be collected before randomization. At this point the research nurse will briefly explain the procedure and familiarize the participant with the Visual Analogue Scale (VAS) system for dyspnea (Appendix I) and pain (Appendix II). Trial treatment will be delivered by means of either a pigtail chest tube (size 10-14 Fr) or PleurX® catheter at bedside after randomization. Outcome measures will be assessed daily until the chest tube is removed and at routine follow-up visits at approximately 14 days, 28 days and three months after the day of procedure as outpatients if the patient has been discharged. While the chest tube is in place, daily symptom assessment will be performed, and daily chest x-ray (PA and lateral when possible) and 24-hour drain output will be recorded (Appendix III) to determine if RSP has been achieved, or if further intervention is indicated.

RSP is defined as chest tube drainage less than 100 cc over the previous 24 hours and a chest x-ray showing similar or decreased pleural space opacification compared to the baseline chest x-ray done the day of pleurodesis (day 0).

Objective determination of the chest x-ray finding will be based on the formal Radiology report in the medical record. If necessary, the findings will be clarified by personal communication between study personnel and the Radiologist reading the film. The algorithm for chest tube and pleural space management after TSP is specified in Figure 2. If RSP is not achieved on day 3, then management will be determined using the algorithm based on the chest x-ray findings and pleural drainage, and may include continued observation, repeat cathflo activase, chest CT, insertion of additional pleural drainage tubes, and repeat TSP with or without cathflo activase. At all follow-up visits after the chest tube has been removed, assessment will include chest x-ray and completion of the VAS for pain and dyspnea.

[figure not shown]
Figure 1. Proposed Workflow of the Trial

Assessments/tasks at visits:

- ◆ VAS scores for pain and SOB
- ◆ Drained volumes in 24 hours if the chest tube is still in place
- ◆ Serum hemoglobin if the chest tube is place
- ◆ CxR (PA and lateral)
- ◆ CT scan, as justified by the PI

Figure 2: Chest Tube Management Algorithm

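### Section 9.1 gives duration of chest tube drainage no stop or censoring rule and 9.2 assigns it a t-test, although the index drain may be a PleurX catheter that has no removal date by the end of follow-up

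*Combined protocol and SAP*

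**What the plan says.** **Device.** Section 8 states: "Trial treatment will be delivered by means of either a pigtail chest tube (size 10-14 Fr) or PleurX® catheter at bedside after randomization". Section 8.3 repeats the choice: "All patients will have a pigtail chest tube (size 10-14) inserted under image guidance, or PleurX® catheter placement". The introduction (3.0) describes PleurX in another role, naming as the two definitive options "either an indwelling catheter to facilitate repeated drainage (e.g. PleurX®) or pleurodesis".

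**Removal.** Under section 8.3 the tube comes out when both day-3 criteria are met (under 100 cc in 24 hours, and a chest x-ray no worse than baseline). Otherwise management follows Figure 2, which is not visible in the public document.

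**Follow-up.** Section 8.2 has one data list for all visits: daily until removal, then 14 days, 28 days and three months. One item is "Drained pleural volumes in 24 hours (if the chest tube is still in place". Section 8 says the later visits are outpatient visits for patients who have been discharged.

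**Outcomes and tests.** Section 9.1 lists "Duration of chest tube drainage" (item 2), repeat pleurodesis (item 5), "Proportion of patients requiring additional chest tube" (item 6) and "Length of hospital stay (in days) after TSP" (item 8). None has a rule for a drain that is still in place. Section 9.2 gives numerical variables a t-test. Its only time-to-event method, the log-rank test, is reserved for symptomatic recurrence after an initial success.

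**The concern.** A t-test needs one number per patient. A patient whose drain is still in at three months, or who dies with it in, has only a lower bound. The analyst must then drop the patient, stop the clock at some convenient date, or count to the end of follow-up. The plan does not choose, so the choice could be made after the data are seen.

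The choice does not affect the arms equally. A retained index drain follows failure on day 3, and the plan expects twice as many such failures in control. The same patients, if discharged with the catheter, have a short stay and no event under items 5 and 6, so those outcomes can understate failure when read alone. This bears on secondary hypothesis 8 (no prolongation of drainage or hospitalization) and on secondary objectives 4, 11 and 12. It matters most where the claim is of no prolongation or no increase, because a masked difference can then pass as reassurance.

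**Working it through.** **1. The plan's own figure.** Inputs from section 6.1: success at day 3 of 60% and 80%, one-sided 5%, 80% power, 5% loss.

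n per arm = [1.645·√(2·0.7·0.3) + 0.842·√(0.6·0.4 + 0.8·0.2)]² / 0.20² = (1.066 + 0.532)² / 0.04 = 63.9, so 64. Then 64/0.95 = 67.4, so 68 per arm and 136 in total. The stated figure is reproduced and nothing below changes it. The 60% and 80% are used in the next steps.

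**2. How many patients could be affected.** Day-3 failures: 0.40·68 = 27.2 in control and 0.20·68 = 13.6 with cathflo, together 40.8 of 136 (30%). The share of these with a PleurX is not stated. For assumed shares:

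| PleurX share of day-3 failures | Control | Cathflo | Total of 136 |
|---|---|---|---|
| 10% | 2.7 | 1.4 | 4.1 (3%) |
| 25% | 6.8 | 3.4 | 10.2 (7.5%) |
| 50% | 13.6 | 6.8 | 20.4 (15%) |

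These are upper counts for each share, since not every PleurX failure need keep the catheter.

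**3. How far the unstated rule moves tube duration.** Assumed, not in the documents: 3 days if day-3 success; 7 days if a failure resolves later; a share s of failures still has the drain at day 90. With f the day-3 failure rate (0.4 or 0.2), the arm mean is:

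- retained patients dropped: [3(1−f) + 7f(1−s)] / (1 − fs)
- clock stopped at an assumed day-4 discharge: 3(1−f) + 7f(1−s) + 4fs
- counted to day 90: 3(1−f) + 7f(1−s) + 90fs

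Example at s = 25%, dropped: control (1.8 + 2.1)/0.90 = 4.33, cathflo (2.4 + 1.05)/0.95 = 3.63, difference 0.70 days. Counted to day 90: 12.90 − 7.95 = 4.95 days.

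| s | Dropped | Stopped at day 4 | Counted to day 90 |
|---|---|---|---|
| 10% | 0.77 | 0.74 | 2.46 |
| 25% | 0.70 | 0.65 | 4.95 |
| 50% | 0.56 | 0.50 | 9.10 |

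(Control minus cathflo, mean days.) Dropping or truncating shrinks the difference as s rises. Counting to the end of follow-up inflates it.

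**4. A second set of assumptions.** Successes: tube out on day 3. Pigtail failures: an extra exponential time with mean 4 days, rounded up, so on average 1/(1−e^(−1/4)) = 4.52 days. PleurX failures: removal time exponential with mean 90 days after day 3. At a PleurX share of one third:

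- all PleurX failures dropped: 0.74 days
- only catheters still in at day 90 dropped: 2.3 days
- all counted, capped at day 90: 0.2·(⅔·4.52 + ⅓·55.8) = 4.3 days, where 55.8 = 90·(1 − e^(−87/90))

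The size differs from step 3, but the dependence on the rule is again large.

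**5. Length of stay under the same assumptions.** Successes and PleurX failures go home on day 4; pigtail failures stay 4.52 days longer on average. The difference is 0.2·(1 − share)·4.52, which gives 0.90, 0.81, 0.68, 0.60 and 0.45 days at shares of 0, 10%, 25%, one third and 50%. Sending every PleurX failure home is the extreme case.

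**The case against.** The strongest reply is that the path is inferred. No section says that a patient who fails pleurodesis goes home with a PleurX. The options listed in sections 8 and 8.3 after a day-3 failure are observation, repeat cathflo, CT, additional drains and repeat pleurodesis. Figure 2 and the study datasheet (Appendix IV) are not visible. Daily x-ray, daily output recording and suction fit an inpatient better than home drainage, and the section 8.2 condition about a drain still in place is generic, because one list serves every visit. This stands: the documents permit a retained catheter at later visits but do not show that the plan expects it. It does not remove the gap, because a management figure or datasheet would not normally supply an analysis rule, and sections 9.1 and 9.2 give none.

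A reader might infer that the plan scores failed pleurodesis as a good result. The documents do not support that. The primary outcome and item 1 of section 9.1 (RSP at any time) still count a patient who never meets the criteria as a failure. A patient discharged on day 4 did have a short stay, and one with no repeat pleurodesis and no added tube is correctly zero on items 5 and 6. What remains is that these items say less than they seem to when read alone.

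The magnitudes also rest on assumed shares and times. At a 10% share only about 4 patients are involved and the length-of-stay difference barely moves. The trial is not powered for these outcomes.

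**Conclusion.** The point holds for duration of chest tube drainage. The outcome has no stop or censoring rule, its assigned test cannot take an incomplete value, and the incomplete values are expected about twice as often in control. Under the assumptions shown, the estimated difference runs from 0.5 to 9.1 days according to the share retained and the rule chosen, and at a fixed 25% share from 0.65 to 4.95 days. These figures show sensitivity to an unwritten rule. They do not predict the trial's result.

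For length of stay, repeat pleurodesis and additional chest tube the point is narrower: the counts are literally correct but can understate failure if patients leave with a catheter. Whether they do, and how many, the documents do not say. About 4 to 20 of 136 is a range under an assumed PleurX share of 10% to 50% of day-3 failures. The primary outcome and the sample size of 136 are unaffected. The change is worth making because it is cheap and should be fixed before unblinding.

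**What to change.** - **Section 9.1, item 2:** define duration as days from TSP to removal of the last drain on the treated side, PleurX included. Score a drain still in place at three months or at death as not removed, with the worst rank, and not as missing.
- **Section 9.2:** compare this outcome between arms by a rank test in place of the t-test, and report medians beside it.
- **Section 9.1, beside items 5, 6 and 8:** report by arm the number discharged with a pleural catheter on the treated side. This is descriptive and does not redefine RSP failure, since such a patient may still reach RSP later.
- **Datasheet:** record device type and removal date, if not already there.

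Cost: a few sentences and at most two data fields, with no extra patients, visits or procedures, and no change to which device is used or when it is removed. Small downside: a rank test gives no difference in mean days, which is why the medians are needed.

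### No outcome counts rescue with cathflo alone, yet RSP reached after it counts as success in two secondary outcomes

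*Combined protocol and SAP*

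**What the plan says.** Section 8 describes management when RSP is not achieved on day 3. It "may include continued observation, repeat cathflo activase, chest CT, insertion of additional pleural drainage tubes, and repeat TSP with or without cathflo activase". Section 8.3 gives a similar list for patients whose tube stays in after the day-3 check, and again names cathflo for undrained fluid separately from repeat TSP.

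In section 9.1, the secondary outcomes that measure rescue are item 5, "Proportion of patients requiring repeat pleurodesis", and item 6, "Proportion of patients requiring additional chest tube". Item 1 is the proportion reaching RSP at any time after TSP, and item 3 is the number of days to RSP. Neither has a condition on treatment given between the randomised instillation and RSP, and section 9.2 adds none. Section 8.2 has repeat pleural interventions recorded at every visit.

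On aftercare, section 8.3 says that the delivery of each treatment and "its aftercare will be provided according to its usual practice protocols and are not specified in this trial". Section 8 says: "The algorithm for chest tube and pleural space management after TSP is specified in Figure 2".

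**The concern.** Of the active rescues that the plan names, one is missing from the outcome list, and it is the drug under test. Two things follow.

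First, a patient who fails at day 3 and is rescued with cathflo alone appears in neither item 5 nor item 6. Section 3.1 says the centre has used cathflo days after talc to break down loculations, so this is not a remote route. Such a dose may avert a repeat pleurodesis. Secondary objective 4 compares repeat pleurodesis between arms, and that comparison is hard to read if the alternative rescue is not reported.

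Second, a placebo patient who fails at day 3, receives cathflo and then reaches RSP is a success under item 1 and supplies a time under item 3. The crossover is invisible, and the success is credited to talc plus placebo. Item 3 serves secondary objectives 7 and 8, on time to RSP in malignant and benign effusion. More control than cathflo-arm patients are expected to need rescue, so the effect is to pull the arms together.

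**Working it through.** **Inputs from section 6.1.** The control rate: "TSP can be expected to produce RSP at three days in approximately 60% of patients". The anticipated rate with cathflo is 80%. The design is to "detect a 20% difference in successful pleurodesis with 80% power", with "a 5% significance level (1-sided) and 5% loss to follow-up", giving 136 patients, 68 per arm.

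**The plan's own figure.** Pooled-variance formula without continuity correction, with mean rate 0.70:

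n = [1.645 × √(2 × 0.70 × 0.30) + 0.842 × √(0.60 × 0.40 + 0.80 × 0.20)]² / 0.20² = 63.9, so 64 per arm.

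64 / 0.95 = 67.4, so 68 per arm and 136 in total. The stated size reproduces exactly. Power with 64 evaluable per arm is 80%.

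**Patients open to rescue.** Without RSP at day 3: 68 × 0.40 = 27.2 control and 68 × 0.20 = 13.6 cathflo-arm patients, about 27 and 14.

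**How each 9.1 outcome treats a day-3 failure given cathflo alone, with RSP later:**

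| Outcome | Score |
|---|---|
| Primary, RSP at day 3 | Failure |
| Item 1, RSP at any time | Success |
| Item 3, days to RSP | The day RSP is reached |
| Item 5, repeat pleurodesis | Not counted |
| Item 6, additional tube | Not counted |

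**Illustration for item 1.** Let r be the share of day-3 failures that reach RSP after cathflo-only rescue. The documents give no value for r, so the values below are assumptions. For simplicity, no one reaches RSP late by any other route. If r is equal in both arms:

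- control rate = 0.60 + 0.40r
- cathflo-arm rate = 0.80 + 0.20r
- difference = 0.20 × (1 − r)

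Power = Φ{[√64 × difference − 1.645 × √(2p̄(1 − p̄))] / √(p₁(1 − p₁) + p₂(1 − p₂))}, one-sided 0.05:

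| r | Control | Cathflo arm | Difference (points) | Power |
|---|---|---|---|---|
| 0 | 60% | 80% | 20 | 80% |
| 0.10 | 64% | 82% | 18 | 75% |
| 0.25 | 70% | 85% | 15 | 65% |
| 0.50 | 80% | 90% | 10 | 48% |

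If such late success occurred in control patients only, r = 0.25 would give 70% against 80% (power 37%), and r = 0.50 would give 80% in both arms. In the equal-share case the ratio of failure rates stays at 2 (40/20, 30/15, 20/10), so it is the absolute difference that shrinks.

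**The case against.** The strongest reply is that the plan already captures most of what matters. Rescue in the text follows failure at day 3, so every such patient is a primary-outcome failure. Cathflo given with repeat TSP is counted under item 5. Objective 4 names repeat pleurodesis and item 5 measures it; a fibrinolytic dose is not a pleurodesis. Cathflo-only rescue could also be tabulated from the data in section 8.2. All of this stands, and it confines the point to secondary outcomes. It does not answer items 1 and 3, which credit RSP after crossover, and data that are collected but tied to no outcome need not be reported.

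A reader might infer that cathflo given before day 3 turns primary failures into successes. The documents do not establish this. Daily review asks whether further intervention is needed, and the text that can be read does not forbid an earlier dose. But that is inference from silence, and Figure 2, which holds the algorithm, is not shown in the text available. Section 3.1 puts the centre's preferred timing at about three days after talc, and section 7.1 says cathflo with TSP is not accepted standard care.

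Scoring any early non-study cathflo as a primary failure is also an estimand choice. Taking day-3 RSP as observed is consistent with the intention-to-treat analysis in section 9.2, so a different rule belongs in a sensitivity analysis.

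Finally, low power on a secondary outcome is not a design error, since section 6.1 sizes the trial on the primary outcome. Nor does every day-3 failure get an active rescue: continued observation is among the listed options.

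**Conclusion.** The point holds for the secondary outcomes. Cathflo alone is a named rescue after day 3, no outcome in 9.1 counts it, and items 1 and 3 credit RSP reached after it. On the planned rates, about 27 control and 14 cathflo-arm patients are exposed to this, and the direction is towards no difference if the drug helps those rescued. The size depends on how often the rescue is used and how often it works, which the documents do not say. The shrinkage and power figures are illustrations under assumed shares and are not properties of the plan.

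It would be too strong to say that such patients are counted as failures nowhere, or that the primary comparison is compromised. By the written pathway they are day-3 failures, and the primary outcome is unaffected. What remains for the primary is a missing statement: neither the RSP definition nor section 9.2 says how non-study cathflo before the day-3 assessment would be handled, if it occurred. The sample-size arithmetic is correct.

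Separately, the wording in 8.3 that aftercare is not specified conflicts with section 8, and with 8.3's own reference to the Figure 2 algorithm.

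**What to change.** 1. In 9.1, add a secondary outcome: any further pleural intervention after the randomised instillation (non-study cathflo, additional tube or repeat TSP), reported by arm with each component.
2. For items 1 and 3, count RSP reached only after such an intervention as not achieved by the randomised treatment, and report RSP regardless of rescue alongside. For item 3, also state how a patient with no qualifying day enters the comparison, since the t-test in 9.2 needs a value for each patient.
3. For the primary outcome, keep the analysis as planned. Report by arm any non-study cathflo given before the day-3 assessment, and add a sensitivity analysis scoring those patients as RSP not achieved.
4. Reconcile the aftercare statements in sections 8 and 8.3. Which aftercare applies is for the investigators.

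The cost is a few sentences in 9.1 and 9.2 and one in 8.3. The outcome in step 1 comes from the repeat pleural interventions already recorded under 8.2. The small downside is that the main RSP-at-any-time rates will be somewhat lower in both arms.
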